9.3.1.2 Primary Analysis

The primary analysis of the primary endpoint will be a within-group treatment comparison in the VX-150 treatment group. The analysis will be conducted using a mixed-effects model for repeated measures (MMRM). The between-group treatment comparison will also be generated using the same MMRM.

The model will include the change from study baseline at each week in the weekly average of daily pain intensity score as the dependent variable; treatment, sex, diagnosis of diabetes, week, and treatment-by-week interaction as fixed effects and baseline pain intensity score as a covariate. The model will be estimated using restricted maximum likelihood. The denominator degrees of freedom for the F-test for fixed effects will be estimated using the Kenward-Roger approximation. In the model, an unstructured covariance matrix will be assumed to model the within-subject variability. If there is a convergence problem due to use of an unstructured covariance matrix, the unstructured covariance matrix will be replaced by a compound symmetric covariance matrix to model the within-subject variability.

Conditional on the observed data and covariates, missing data will be assumed to be missing at random; consequently, no imputation of missing data will be performed.

The post-baseline raw values and the change from baseline at each week will be summarized descriptively (n, mean, SD, SE, median, minimum, and maximum).

The adjusted mean (SE), corresponding 95% 2-sided confidence interval (CI) and 2-sided *P* value for VX-150 treatment group in change from study baseline in weekly average of daily NRS at Week 6 will be provided. The CI will first be used to facilitate the comparison with 0; this will be followed by a comparison with 0.8. Furthermore, the adjusted mean (SE) and corresponding 95% CI for the treatment difference between VX-150 and placebo at Week 6 will be provided.

In addition, adjusted means (SE) and 95% CIs for all within-group treatment and between-group treatment comparisons at other weeks will also be provided.

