8.1 Inclusion Criteria

- 1. Subject will sign and date an informed consent form (ICF)
- 2. Willing and able to comply with scheduled visits, treatment plan, study restrictions, laboratory tests, contraceptive guidelines, and other study procedures
- 3. Subjects (male and female) will be between the ages of 18 and 80 years, inclusive.
- 4. Body mass index (BMI) of \geq 18.0 kg/m²
- 5. Diagnosis of small fiber neuropathy, as per European Federation Neurological Societies (EFNS)/American Academy of Neurology (AAN) guidelines, with pain for at least 3 months prior to screening
- 6. Reduction below the 5th percentile of sex and age-adjusted normal values in epidermal nerve fiber density on punch skin biopsy at the distal site of the leg performed at screening
- 7. Presence of sural nerve responses
- 8. Average NRS score between ≥ 4 and ≤ 9 reported in the daily diary on Days -7 through -1

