12.3.3.1 Analysis of Primary Variable

The primary efficacy endpoint is the change from baseline in the weekly average of daily pain intensity on the 11-point NRS, as reported in the daily diary, at Week 6.

The primary analysis of the primary endpoint will be a within-group treatment comparison in the VX-150 treatment group. The analysis will be conducted using a mixed-effects model for repeated measures (MMRM). The between-group treatment comparison will also be generated using the same MMRM. The model will include the change from study baseline in the weekly average of daily pain intensity score as the dependent variable; treatment, sex, diagnosis of diabetes, week, and treatment-by-week interaction as fixed effects; subject as a random effect; and baseline pain intensity score as a covariate. In the model, week will be treated as a class variable, and an unstructured covariance matrix will be assumed to model the within-subject variability. The denominator degrees of freedom for the F-test for fixed effects will be estimated using the Kenward-Roger approximation.

The estimated mean and corresponding 95% CI for VX-150 will be provided for the withingroup change. The CI will first be used to facilitate the comparison with 0; this will be followed by a comparison with 0.8. In addition, the estimated mean and corresponding 95% CI for the between-group difference will be provided.

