7.2 Sample Size and Power

The primary efficacy endpoint is the change from baseline in the weekly average of daily pain intensity on the 11-point NRS, as reported in the daily diary, at Week 6. The primary analysis of the primary efficacy endpoint will be a within-group treatment comparison in the VX-150 treatment group. The 95% CI for the within-group change will be used to evaluate if there is any significant change from baseline (within-group change against 0). Additional analyses will include an evaluation of this within-group change against 0.8, an expected change from the placebo group, and a 95% CI for the between-group comparison of change from baseline.

Assuming a within-group change of 0.8 for placebo and a between-group treatment difference of 1.25, the expected within-group change for VX-150 is 2.05. With an SD of 2.08, the power for the 95% CI for the within-group change to rule out 0 or 0.8 is summarized in for 25, 35, or 45 evaluable subjects per group. The power for the 95% CI for the between-group treatment difference to rule out 0 is also provided. In order to allow for withdrawal of up to 20% of randomized subjects over 6 weeks of treatment, the study will enroll and randomize a minimum of approximately 62 subjects (25 evaluable subjects per group) and up to approximately 114 subjects (45 evaluable subjects per group) in total.

Table 7-2 Power for the 95% Confidence Intervals for Within- and Between-group Changes

Number of Evaluable Subjects Per Group	Power for the 95% CI for the Within-group Change to Rule out 0	Power for the 95% CI for the Within-group Change to Rule Out 0.8	Power for the 95% CI for the Between-group Treatment Difference to Rule Out 0
25	> 99%	82%	55%
35	> 99%	93%	70%
45	> 99%	98%	81%

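### The primary analysis tests the VX-150 arm's own change from baseline against 0, not against the randomised placebo arm; on the plan's assumptions an inert drug passes that test in 45% to 71% of trials

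*SAP*

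**What the plan says.** SAP 9.3.1.2 defines the primary analysis: "The primary analysis of the primary endpoint will be a within-group treatment comparison in the VX-150 treatment group". Protocol 12.3.3.1, protocol 12.1 and the synopsis agree, so this is a deliberate choice and not a slip in one place.

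SAP 7.2 gives the null value: "The 95% CI for the within-group change will be used to evaluate if there is any significant change from baseline (within-group change against 0"). The same section classes two further evaluations as additional: the VX-150 change against 0.8, and the 95% CI for the between-group comparison.

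The planning assumptions are in SAP 7.2 and protocol 12.1: "Assuming a within-group change of 0.8 for placebo and a between-group treatment difference of 1.25, the expected within-group change for VX-150 is 2.05".

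On the placebo comparison, protocol 12.3.3.1 says: "The between-group treatment comparison will also be generated using the same MMRM". SAP 9.3.1.2 asks for a two-sided P value for the VX-150 within-group change. For the VX-150 minus placebo difference it asks only for an adjusted mean, SE and 95% CI. SAP 9.1 plans no multiplicity adjustment, and neither document states a success rule that ties the three comparisons together.

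**The concern.** The primary objective is the efficacy of VX-150, and placebo is randomised and blinded so that drug effect can be separated from everything else that moves pain scores. A test of the VX-150 arm against 0 does not use that separation. It asks whether treated subjects improved, and the plan already expects untreated subjects to improve.

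Regression to the mean is one plausible source of such improvement. Entry requires an average NRS of 4 to 9 "reported in the daily diary on Days -7 through -1" (protocol 8.1), and the average over those same days is the baseline (protocol 12.3.1, SAP 9.1). This is best read as a possible component of the placebo change, not as something on top of it. The documents do not give its size.

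If the plan stands, the trial can be positive on its primary analysis while VX-150 does no better than placebo. The headline power of above 99% then refers to a hypothesis that does not test efficacy.

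**Working it through.** **Inputs** (SAP 7.2 and 9.3.1.2; the same values are in protocol 12.1)
- Placebo change 0.8; between-group difference 1.25; VX-150 change 0.8 + 1.25 = 2.05.
- SD of change 2.08.
- Evaluable n per group: 25, 35 or 45; allocation 1:1.
- A "corresponding 95% 2-sided confidence interval (CI"), so 2.5% in the direction of benefit.

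Improvements are written as positive numbers, as in the sample-size sections. SAP 9.1 defines change as post-baseline minus baseline, so improvements will be negative in the data; this does not affect the arithmetic.

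**Formulas**
- Within-group: SE = 2.08/√n, noncentrality = d/SE, noncentral t with n − 1 df, where d is the true change minus the reference value.
- Between-group: SE = 2.08 × √(2/n), noncentrality = 1.25/SE, noncentral t with 2n − 2 df.

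**Step 1. Reproduce the plan's power table** (protocol Table 12-1, SAP Table 7-2). Stated values are in brackets.

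| n per group | Against 0 (d = 2.05) | Against 0.8 (d = 1.25) | Between groups (1.25) |
|---|---|---|---|
| 25 | 99.7% (>99%) | 82.2% (82%) | 54.9% (55%) |
| 35 | 99.99% (>99%) | 93.2% (93%) | 69.8% (70%) |
| 45 | >99.99% (>99%) | 97.6% (98%) | 80.5% (81%) |

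The table reproduces, so the method matches the plan's.

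**Step 2. Primary test with an inert drug.** Its true change equals the assumed placebo change, so d = 0.8 against 0.

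| n | SE | Noncentrality 0.8/SE | Critical t | P(CI excludes 0, benefit) |
|---|---|---|---|---|
| 25 | 0.416 | 1.92 | 2.064 | 45.5% |
| 35 | 0.352 | 2.28 | 2.032 | 59.9% |
| 45 | 0.310 | 2.58 | 2.015 | 71.3% |

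At n = 45 an observed change of about 2.015 × 0.310 = 0.62 already excludes 0, and that is smaller than the change expected on placebo. The false-pass rate rises with n, so enrolling more subjects makes it worse.

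Pooled degrees of freedom (2n − 2) give 47.0%, 61.2% and 72.3%. A normal approximation gives 48.5%, 62.4% and 73.2%.

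**Step 3. The additional comparison with 0.8.** For an inert drug, d = true placebo change − 0.8. The plan's value is 0.8; the other true changes are assumptions used to show sensitivity.

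| True placebo change | n = 25 | n = 35 | n = 45 |
|---|---|---|---|
| 0.4 (assumed) | 0.2% | 0.1% | 0.06% |
| 0.8 (plan) | 2.5% | 2.5% | 2.5% |
| 1.2 (assumed) | 15% | 20% | 24% |
| 1.6 (assumed) | 45% | 60% | 71% |

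**Step 4. The between-group interval.** With an inert drug the true difference is 0 whatever the placebo response, so it excludes 0 in the direction of benefit 2.5% of the time at every n.

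**The case against.** The strongest defence is that the placebo arm is not ignored. One MMRM is fitted to both arms, the adjusted VX-150 minus placebo difference with its 95% CI is prespecified at Week 6 and at the other weeks, and its power is published beside the others. Any reader of the report will see it. This is correct. The complaint is about the contrast that carries the primary conclusion: the placebo comparison lacks primary status and a named P value.

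Second, neither document states a go/no-go rule, and the interval is to be read against 0 and then against 0.8. If both steps were required and the true placebo change were exactly 0.8, an inert drug would clear both only 2.5% of the time. The 45% to 71% therefore belongs to the designated primary step and is not shown to be the false-positive rate of whatever decision the sponsor finally takes. But both sample-size sections call the 0.8 step additional, nothing makes it mandatory, and it treats an assumed placebo response as known when the trial measures that response. A fixed 0.8 can err either way: it is too strict if placebo subjects improve less and too lenient if they improve more.

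Third, this is a Phase 2 proof-of-concept study and the choice is explicit. That can justify modest power. It does not justify a primary test that cannot separate drug effect from placebo response.

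**Conclusion.** The concern holds and needs correcting. As written, the primary analysis does not test the primary objective, and a positive result could not be attributed to VX-150. On the plan's own inputs, an inert drug meets the primary criterion in 45%, 60% and 71% of trials at 25, 35 and 45 evaluable subjects per group.

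These figures take meeting the criterion to mean that the 95% CI excludes 0 in the direction of benefit. They rest on a placebo change of 0.8, an SD of 2.08 and a one-sample t calculation. If the true placebo change were 0.4 (an assumption), the rates would be 15% to 24%; at 1.2 (also an assumption), 79% to 97%. Baseline adjustment in the MMRM could reduce the residual SD and push the rates higher. The conclusion about attribution does not depend on the exact figure: any real placebo improvement makes 0 the wrong reference value.

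**What to change.** In protocol 12.1 and 12.3.3.1, the protocol synopsis, and SAP 7.2 and 9.3.1.2:

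- Name the VX-150 minus placebo difference at Week 6, from the planned MMRM, as the primary analysis, reported with its 95% CI and two-sided P value.
- Keep the within-group changes against 0 and 0.8 as descriptive or supportive results.
- Quote the between-group column of the power table as the study's power.

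The planned model already produces this contrast, so no new data or model is needed. The change is one of wording, but it is a protocol modification and goes through the notifications in protocol 13.2.3.

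The real cost is in the stated power, which falls from above 99% to 55%, 70% or 81% at 25, 35 or 45 evaluable per group. The planned maximum of about 114 randomised (114 × 0.8 / 2 = 45.6 evaluable per group) supports about 80% without further subjects. The permitted minimum of about 62 (62 × 0.8 / 2 = 24.8 per group) gives only about 55%. The sponsor should say whether that is acceptable for the new primary analysis or plan to enrol towards the maximum.

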9.3.2.2 Secondary Analyses

Proportion of subjects with $\geq 30\%$ reduction in the weekly average of daily pain intensity on the 11-point NRS, as reported in the daily diary, at Week 6: This variable will be evaluated using descriptive statistics by treatment group.

[figure not shown]
Proportion of subjects with $\geq 50\%$ reduction in the weekly average of daily pain intensity on the 11-point NRS, as reported in the daily diary, at Week 6: Analysis of this variable will be the same as described for proportion of subjects with $\geq 30\%$ reduction.

[figure not shown]
In addition, the proportion of subjects with $\geq 70\%$ reduction in the weekly average of daily pain intensity at Week 6 will also be analyzed in the same way as described for the proportion of subjects with $\geq 30\%$ reduction.

Change from baseline in the DSIS at Week 6: Analysis of this variable will be based on an MMRM similar to the analysis of the primary efficacy variable. Weekly average of daily DSIS score at each week will be included in the model as the dependent variable.

Proportion of subjects categorized as improved at Week 6 on the PGIC assessment: This variable will be evaluated using descriptive statistics by treatment group.

Change from baseline in pain intensity on the 11-point NRS, as reported at study visits, at Week 6: Analysis of this variable will be based on an MMRM similar to the analysis of the primary efficacy variable. The change from baseline in NRS at each post-baseline visit (Day 7, Week 3 and Week 6) will be included in the model as the dependent variable.

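### If the unstructured covariance fails to converge, the only fallback is homogeneous compound symmetry, which gives a wrong Week 6 standard error whenever the variance of change differs by week

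*SAP*

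**What the plan says.** SAP section 9.3.1.2 sets up the primary model as follows.

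- Outcome: "The model will include the change from study baseline at each week in the weekly average of daily pain intensity score as the dependent variable". SAP Appendix A defines six weekly windows, Days 1–7 to Days 36–42.
- Covariance: "In the model, an unstructured covariance matrix will be assumed to model the within-subject variability".
- Estimation: "The model will be estimated using restricted maximum likelihood".
- Degrees of freedom: "The denominator degrees of freedom for the F-test for fixed effects will be estimated using the Kenward-Roger approximation".
- Fallback: "If there is a convergence problem due to use of an unstructured covariance matrix", then "the unstructured covariance matrix will be replaced by a compound symmetric covariance matrix".

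No other structure is listed, no attempt to restore convergence comes first, and no empirical (sandwich) standard error is named. Protocol section 12.3.3.1 specifies the unstructured matrix and has no fallback, so the SAP sentence is the only rule.

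For the DSIS and for the NRS reported at visits, SAP section 9.3.2.2 says: "Analysis of this variable will be based on an MMRM similar to the analysis of the primary efficacy variable". It does not repeat the covariance rule, but the natural reading is that the fallback carries over.

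**The concern.** With six weeks, an unstructured matrix has 6 variances and 15 covariances, 21 parameters in all. Homogeneous compound symmetry has 2: one variance and one covariance shared by all weeks. The primary endpoint is at Week 6 only, and under compound symmetry its standard error comes from a variance pooled over Weeks 1 to 6. If the Week 6 variance is above that average, the interval is too narrow; if below, too wide. Kenward-Roger is a small-sample adjustment within the assumed structure and does not correct a wrong one.

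Rising variance is plausible in this design. Baseline is the average of Days -7 to -1, right beside Week 1 and five weeks further from Week 6, and the model adjusts for baseline. If weekly pain scores are serially correlated, Week 1 is better predicted by baseline than Week 6 is. This is an argument from design, not a figure in the documents.

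At stake, if the fallback is used, are the Week 6 intervals: the within-group change against 0 and 0.8, and the between-group difference.

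**Working it through.** **Inputs from the plan** (SAP section 7.2, Protocol section 12.1): SD of change 2.08, a single value; expected change 2.05 on VX-150 and 0.8 on placebo, difference 1.25; 25 to 45 evaluable per group; up to 20% withdrawal; 95% two-sided intervals.

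**Assumed, not in the documents:** the weekly SDs. I take 2.08 as the Week 6 SD and a straight line from a Week 1 value to 2.08.

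**1. The plan's own figures.** With noncentral t and two-sided alpha 0.05, power at n = 25, 35 and 45 per group is:

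- against 0: 99.7%, >99.9%, >99.9% (plan: >99% throughout);
- against 0.8: 82.2%, 93.2%, 97.6% (plan: 82%, 93%, 98%);
- between groups: 54.9%, 69.8%, 80.5% (plan: 55%, 70%, 81%).

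For numbers randomized, 50/0.8 = 62.5 and 90/0.8 = 112.5 (57 per arm, 114 in total). The planning table is reproduced.

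**2. Correct Week 6 standard errors at SD 2.08.** Within group: 2.08/√25 = 0.416 and 2.08/√45 = 0.310. Between groups: 2.08·√(2/25) = 0.588 and 2.08·√(2/45) = 0.439.

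**3. The same under compound symmetry, complete data.**

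- Ratio of model SE to true SE = √(mean of the six weekly variances) / 2.08.
- Type I error = 2·[1 − Φ(1.96 × ratio)].

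Example, Week 1 SD 1.0: the SDs are 1.0, 1.216, 1.432, 1.648, 1.864 and 2.08. Their squares sum to 15.046, the mean is 2.508 and its root is 1.584. The ratio is 1.584/2.08 = 0.761, and 1.96 × 0.761 = 1.492 gives 13.6%.

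| Week 1 SD (assumed) | Pooled SD | SE ratio | Coverage | Type I error | Between-group SE, n = 25 | Between-group SE, n = 45 |
|---|---|---|---|---|---|---|
| 2.6 (falling) | 2.347 | 1.13 | 97.3% | 2.7% | 0.664 | 0.495 |
| 2.08 (constant) | 2.080 | 1.00 | 95.0% | 5.0% | 0.588 | 0.439 |
| 1.8 | 1.942 | 0.93 | 93.3% | 6.7% | 0.549 | 0.409 |
| 1.6 | 1.847 | 0.89 | 91.8% | 8.2% | 0.522 | 0.389 |
| 1.5 | 1.801 | 0.87 | 91.0% | 9.0% | 0.509 | 0.380 |
| 1.2 | 1.667 | 0.80 | 88.4% | 11.6% | 0.472 | 0.352 |
| 1.0 | 1.584 | 0.76 | 86.4% | 13.6% | 0.448 | 0.334 |

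**4. Simulation check.** REML compound-symmetric fits with treatment-by-week, sex, diabetes and baseline; 1,500 runs per setting; true correlation either constant at 0.7 or AR(1) at 0.85; a t reference with large degrees of freedom in place of Kenward-Roger. Between-group type I error:

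- 45 per arm, complete data: 4.4–4.9% (constant SD), 8.3–9.1% (from 1.6), 11.5% (from 1.2).
- 57 per arm, 20% random dropout: 4.3–5.2%, 8.3–10.0% and 11.9–13.9%.

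These agree with the formula, with slightly more inflation under dropout.

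**5. Which assumed range is plausible?** If raw weekly scores have constant variance and week-to-week correlation ρ, the variance at week k given baseline is proportional to 1 − ρ^(2k). Scaled to 2.08 at Week 6, ρ = 0.7, 0.8 and 0.9 imply Week 1 SDs of 1.50, 1.29 and 1.07. The variance path is then curved, not linear, and the type I error is 7.0%, 8.4% and 10.5%.

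**6. Which results are exposed?** At the planned effect, estimate/SE with the correct SE and with the worst SE in the table (Week 1 SD 1.0), n = 25:

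- against 0: 2.05/0.416 = 4.9, and 2.05/0.317 = 6.5. The conclusion is the same.
- against 0.8: 1.25/0.416 = 3.0, and 1.25/0.317 = 3.9.
- between groups: 1.25/0.588 = 2.1, and 1.25/0.448 = 2.8. A borderline result would look firm.

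**The case against.** The strongest reply is that the rule will probably never be used. Under AR(1) correlation 0.8 and 20% random dropout, unstructured REML fits to simulated data converged with a positive-definite matrix in 278 of 278 runs: 100 with 62 subjects and Week 1 SD 1.0, 100 with 62 subjects and SD 1.5, and 78 with 114 subjects and SD 1.0. The SAP also drops the random subject effect that the Protocol lists beside the unstructured matrix, which removes a redundant term and a likely source of trouble. This stands as evidence that failure is unlikely. It does not show that failure is impossible, because the optimiser was not SAS and the dropout was unrelated to outcome.

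Two more replies stand. The weekly SDs are unknown, so the direction of the error is unproven. And section 9.3.1.2 requires the raw SD and SE at each week to be reported, so a model SE well below the raw Week 6 SE would be noticed. Noticing it after unblinding, however, leaves no pre-specified remedy.

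A reader might infer that the Week 6 intervals will be too narrow and the type I error inflated, or that the fallback would decide the primary result. The documents support neither. The first needs both non-convergence and rising variance, and falling variance makes the test conservative. The second overlooks that the primary comparison with 0 has more than 99% planned power and barely depends on the covariance structure at the planned effect.

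The secondary models are less exposed than the primary wording suggests. The visit NRS model has three time points and so 6 unstructured parameters, and failure there is very unlikely.

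**Conclusion.** The point holds as a conditional one. If the unstructured fit fails and the variance of change differs by week, homogeneous compound symmetry gives a wrong Week 6 standard error. On the assumed linear rise to 2.08, the type I error runs from about 6.7% (Week 1 SD 1.8) to 13.6% (Week 1 SD 1.0), against 5% with constant SD. With an SD falling from 2.6 it is about 2.7%. The comparison with 0.8 and the between-group interval are the results at risk.

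The mechanism is certain. The likelihood of the trigger and the weekly SDs cannot be read from the documents. There is also an unmeasured effect: the plan assumes data missing at random, and under such dropout a wrong covariance can bias the Week 6 mean as well as its standard error. The simulations used dropout unrelated to outcome and say nothing about the size of that bias.

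This is a cheap improvement of low priority.

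**What to change.** Replace the fallback sentence in SAP section 9.3.1.2, before database lock, with an ordered list:

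1. If the unstructured fit does not converge, try heterogeneous Toeplitz, then heterogeneous AR(1), then heterogeneous compound symmetry. Use the first that converges, keeping REML and Kenward-Roger.
2. Use homogeneous compound symmetry only if all of these fail. In that case report an empirical (sandwich) standard error and name a small-sample degrees-of-freedom method to replace Kenward-Roger, since there may be only 25 evaluable subjects per group.

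State in section 9.3.2.2 that the same order applies to the DSIS model and, for completeness, to the visit NRS model.

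Limits of the remedy: the sandwich step repairs the standard error but not any bias in the Week 6 mean from a wrong covariance under missing-at-random dropout, which is why it comes last. Heterogeneous AR(1) gave a type I error of about 3% to 6% in 300 simulated runs per setting, but only where it was the true structure. Heterogeneous Toeplitz was not simulated. The exact order is therefore a matter of judgement; keeping a separate Week 6 variance is the essential part.

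Cost: one changed sentence, one cross-reference, and a few more covariance parameters than compound symmetry if the fallback is triggered. Nothing changes if the unstructured model converges.
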